3.1.1 Screening Period

The screening period of up to 4 weeks is intended to allow sufficient time for a patient to meet all eligibility requirements. Patients must complete at least 12 days of the screening period to demonstrate eDiary compliance (see Section 4.1.1.1). Patients who are unable to complete assessments or meet eligibility requirements during the screening period will be permitted to be re-screened once for a total of up to two times. Within a screening period, patients who do not meet the requirement of pre-bronchodilator FEV₁ of 40%–80% or post-bronchodilator reversibility of FEV₁ (liters) of $\geq 12\%$ and ≥ 200 mL are allowed up to two additional attempts to meet these two eligibility criteria, but only if their pre-bronchodilator FEV₁ was between 35% and 85%.

Patients who rescreen ≤ 6 weeks after Informed Consent Form completion must only repeat the assessments that triggered screen failure. Patients who rescreen >6 weeks after Informed Consent Form completion are required to repeat the consent process and all screening assessments except tuberculosis (TB) screening and hepatitis serologies. However, TB screening and hepatitis serologies should be repeated if the re-screening takes place >6 months after initial screening or if there is risk of exposure.

3.1.2 Run-In Period

Patients enrolled in the run-in period will receive one single-blind dose of placebo at the run-in visit (Week 0). eDiary compliance must continue to be demonstrated on at least 5 of 7 days during each of the 2 consecutive weeks of the run-in period (see Section 4.1.1.2). Patients who do not meet eligibility criteria for the double-blind treatment period will be discontinued from the study and are not eligible for rescreening (see Section 4.6.2).

3.1.3 Internal Monitoring Committee

Periodic safety reviews will be performed by the Sponsor's Internal Monitoring Committee (IMC) as outlined in the IMC Charter. This committee will be unblinded to treatment assignments and will include a clinical scientist, drug safety scientist, biostatistician, and statistical programmer from the Sponsor. The IMC members will not have direct contact with investigational staff or site monitors. The IMC may decide to unblind the study team to enable decision-making. The IMC may invite representatives from other functional areas on an ad-hoc basis when additional expertise is required (e.g., clinical pharmacology, research) or invite additional Sponsor scientists to participate in data analyses and review.

The IMC will meet at a frequency dictated by the IMC charter but no less frequently than once every 3 months. Additionally, ad-hoc IMC meetings may be convened immediately or expeditiously at any time to address potential safety concerns if periodic review of blinded safety data indicates 3 or more patients with serious or Grade 3 or higher adverse events (excluding asthma exacerbations) that the investigator or Sponsor determines to be related to study treatment, within the same MedDRA high level term.

The IMC will assess the severity, relatedness, and reversibility of adverse events, the degree of imbalance between treatment arms, the similarity and frequency of events under a single higher level term, the plausibility of a common mechanism, possible risk mitigation measures, and may recommend changes to study conduct (including termination of study) as appropriate.

At any time during the study, the Sponsor may choose to inactivate and suspend enrollment and further dosing or reduce the dose due to safety concerns as recommended by the IMC. Should an ad-hoc IMC meeting be convened, enrollment of patients may be temporarily halted if warranted by the frequency and severity of the blinded adverse events, until the IMC evaluates the unblinded data and decides whether resumption of dosing is safe to proceed, or until IMC-recommended changes to the conduct of the study are implemented.

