2.1 EFFICACY OBJECTIVES

2.1.1 Primary Efficacy Objective

The primary efficacy objective for this study is to evaluate the efficacy of MTPS9579A compared with placebo on the basis of the following endpoint:

- Time to first CompEx event (Fuhlbrigge et al. 2017), a composite endpoint defined as time from randomization to first asthma exacerbation or diary worsening during the 48-week double-blind treatment period (from the randomization visit [Week 2] to end of treatment [Week 50]). Asthma exacerbations and diary worsening are defined as follows:

Asthma exacerbations are assessed by the investigator and defined as new or increased asthma symptoms (wheezing, coughing, dyspnea, chest tightness, and/or nighttime awakenings due to these symptoms) that result in one or both of the following:

- Hospitalization or an emergency department or urgent care visit requiring administration of systemic corticosteroid treatment
- Treatment with systemic (IV, intramuscular [IM], or oral) corticosteroids for ≥ 3 days or a long-acting depot corticosteroid preparation with a therapeutic effectiveness of ≥ 3 days
- Diary worsening is based on the occurrence of prespecified changes (deteriorations) in a subset of the following six parameters: morning peak expiratory flow rate (PEFR), evening PEFR, morning symptom score, evening symptom score, morning short-acting rescue therapy use, and evening short-acting rescue therapy use. A detailed definition of diary worsening is provided in Section 6.4.1.

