4.6 TREATMENT, PATIENT, STUDY, AND SITE DISCONTINUATION

4.6.1 Study Treatment Discontinuation

Patients must permanently discontinue study treatment if they experience any of the following:

- Any medical condition that the investigator or Sponsor determines may jeopardize the patient's safety if he or she continues to receive study treatment
- Any Grade 4 adverse event that the investigator or Sponsor determines to be related to study treatment. This excludes asthma exacerbations, unless they meet one of the other criteria for study treatment discontinuation.

- Investigator or Sponsor determination that treatment discontinuation is in the best interest of the patient
- Pregnancy
- Suspicion of hypersensitivity or anaphylactic reaction to study drug (i.e., generalized urticaria or angioedema [WHO Grade 3 allergic reaction] or anaphylaxis [Grade 4 allergic reaction] related to study drug, or Grade 3 or 4 infusion related reaction)

The primary reason for study treatment discontinuation should be documented on the appropriate eCRF. Patients who discontinue study treatment prematurely will not be replaced and should continue follow-up for all other study procedures and measurements through the end of the study (Week 58).

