5.1.1.2 Hypersensitivity/Hypersensitivity-Like Reactions and Anaphylaxis/Anaphylactoid Reactions

Hypersensitivity reactions and anaphylaxis have been described with SC or IV administration of monoclonal antibodies (Corominas et al. 2014). Signs and symptoms may include acute onset (minutes to several hours) of one or more of the following: respiratory compromise, reduced blood pressure, skin-mucosal involvement, or gastrointestinal symptoms (Sampson et al. 2006). See [Appendix 6](#) for anaphylaxis precautions and management.

No hypersensitivity/hypersensitivity-like reactions or anaphylaxis/anaphylactoid reactions associated with MTPS9579A were observed following a single IV dose or repeat IV and SC doses in cynomolgus monkeys. The potential for hypersensitivity to MTPS9579A in humans is unknown. However, to date, there have been no reports of anaphylaxis or systemic hypersensitivity among subjects enrolled in the Phase I clinical trial of MTPS9579A in healthy volunteers, even among those who developed ADAs.

Systemic allergic reactions have also not been observed in the Phase I clinical study in healthy volunteers. However, as with any large-molecule therapeutic, administration of MTPS9579A may result in systemic reactions. Systemic reactions to large-molecule therapeutics can be IgE mediated; however, they may also be non-IgE mediated or due to cytokine release. Systemic reactions are generally characterized by signs and symptoms that include skin rash, urticaria, pruritus, local or diffuse erythema, angioedema, fever, chills, cough, dyspnea, wheezing, bronchospasm, nausea, vomiting, diaphoresis, chest pain, tachycardia or bradycardia, and/or hypotension, which can be severe or life threatening. Effects typically occur during drug administration, or within several hours of administration, but they may be delayed.

Patients with a history of anaphylaxis, hypersensitivities, or drug allergies to antibody therapeutics will be excluded from studies with MTPS9579A.

Investigators and healthcare professionals administering MTPS9579A should be trained to recognize and manage the signs and symptoms of a potential anaphylactic,

anaphylactoid, or hypersensitivity reaction and should be familiar with Sampson's criteria for defining anaphylaxis (Sampson et al. 2006; see [Appendix 6](#)).

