5.6 ADVERSE EVENTS THAT OCCUR AFTER THE ADVERSE EVENT REPORTING PERIOD

The Sponsor should be notified if the investigator becomes aware of any serious adverse event that occurs after the end of the adverse event reporting period (defined as 84 days after the final dose of study drug or end of study (Week 58) for patients who discontinue study drug but remain on study, or 6 weeks following the placebo dose for patients who failed to be randomized), if the event is believed to be related to prior study drug treatment. These events should be reported through use of the Adverse Event eCRF. However, if the EDC system is not available, the investigator should report these events directly to the Sponsor or its designee, either by faxing or by scanning and emailing the paper Clinical Trial Serious Adverse Event/Adverse Event of Special Interest Reporting Form using the fax number or email address provided to investigators.

5.7 EXPEDITED REPORTING TO HEALTH AUTHORITIES, INVESTIGATORS, INSTITUTIONAL REVIEW BOARDS, AND ETHICS COMMITTEES

The Sponsor will promptly evaluate all serious adverse events and adverse events of special interest against cumulative product experience to identify and expeditiously communicate possible new safety findings to investigators, IRBs, ECs, and applicable health authorities based on applicable legislation.

To determine reporting requirements for single adverse event cases, the Sponsor will assess the expectedness of these events using the following reference document:

- MTPS9579A Investigator's Brochure

The Sponsor will compare the severity of each event and the cumulative event frequency reported for the study with the severity and frequency reported in the applicable reference document.

Reporting requirements will also be based on the investigator's assessment of causality and seriousness, with allowance for upgrading by the Sponsor as needed.

An IMC will monitor the incidence of the above-listed anticipated events during the study (see Section 3.1.3).

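### The one written ad hoc IMC trigger leaves out asthma exacerbations even when they are judged drug-related, so such an event may wait for the next periodic review

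*Protocol*

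**What the plan says.** Protocol Section 3.1.3, with the same text in the synopsis, states that "ad-hoc IMC meetings may be convened immediately or expeditiously at any time to address potential safety concerns". The stated condition is that blinded safety review shows at least three patients, within one MedDRA high level term, with "serious or Grade 3 or higher adverse events (excluding asthma exacerbations) that the investigator or Sponsor determines to be related to study treatment". No exception is written for an exacerbation that has been judged related.

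Separately, the unblinded IMC meets at least every 3 months and looks at adverse events, relatedness and imbalance between arms. The exclusion is not repeated for that review.

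Section 2.1.1 defines an exacerbation as new or increased asthma symptoms plus a treatment consequence, one form of which is "Hospitalization or an emergency department or urgent care visit requiring administration of systemic corticosteroid treatment". Section 5.1.1.2 describes systemic reactions to large-molecule drugs by signs that include "angioedema, fever, chills, cough, dyspnea, wheezing, bronchospasm", and says that onset may be delayed.

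Section 4.6.1 excludes exacerbations from the related Grade 4 criterion for stopping treatment, with a qualification: "This excludes asthma exacerbations, unless they meet one of the other criteria for study treatment discontinuation". Section 5.7 closes with "An IMC will monitor the incidence of the above-listed anticipated events during the study", but no list of anticipated events appears in that section.

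**The concern.** The trigger applies two filters. The first keeps only events judged related to study treatment. Exacerbations attributed to the patient's asthma do not pass it, because Table 4 in Section 5.3.4 names underlying disease as an alternative cause. The second filter removes exacerbations whatever the attribution. After the first filter has acted, what the second removes is mainly the exacerbations that the investigator or Sponsor has judged to be drug-related.

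In an asthma trial this is the overlap that matters. A drug reaction in the airway and a worsening of asthma can present with the same symptoms and be treated with the same class of drug, and Section 1.3 says that risks in patients with asthma are unknown. A cluster of related airway events recorded as exacerbations would not meet the written condition for an early meeting. Section 4.6.3 also points back to 3.1.3 when it lists aggregate safety signals among the reasons for ending the study.

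**Working it through.** The documents give no operating characteristic for the trigger, so there is no figure to reproduce. The check is a reading of the recording rules, followed by an illustration.

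**1. How a related airway event is recorded**

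| Timing | Governing text | Recorded as | Can it count toward the ad hoc trigger? |
|---|---|---|---|
| During or within 24 h of infusion, not meeting the exacerbation definition | 5.3.5.1 | Individual signs and symptoms; acute bronchospasm has its own line in Appendix 7 | Yes |
| Within 24 h, also meeting the definition in 2.1.1 | 5.3.5.1 (symptoms) and 4.5.12 (report the exacerbation as an adverse event) | Not stated which governs | Unclear |
| After 24 h, judged an exacerbation | 5.3.5.2 (a diagnosis, if known) and 5.3.5.10 (suggested descriptor) | Asthma exacerbation | No |
| Death attributed solely to exacerbation | 5.3.5.8 | Asthma exacerbation | No |

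The gap is therefore the last three rows.

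**2. Possible delay**

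Periodic reviews are at most 3 months apart (3.1.3), or about 13 weeks. Infusions are every 4 weeks (3.1). 13/4 = 3.25, so about three infusions for a patient still on treatment could fall between two reviews. This is an upper limit; the IMC Charter may set a shorter interval.

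**3. Illustration of the count**

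Inputs: n = 69 safety-evaluable patients on active drug (SAP Output 1.1); threshold of 3 patients (3.1.3). Assumptions not in the documents: the true risk p per patient of a related serious or Grade 3+ airway event, and the share f of these events recorded as exacerbations. All events are taken to share one high level term.

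P(X ≥ 3) = 1 − Σ(k = 0 to 2) C(69, k) q^k (1 − q)^(69 − k), with q = p(1 − f).

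For p = 0.05 and f = 0 the three terms are 0.0290 + 0.1054 + 0.1887 = 0.3231, so P = 0.677. The other cells follow in the same way:

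| Assumed p | f = 0 | f = 0.5 | f = 1 |
|---|---|---|---|
| 1% | 0.032 | 0.005 | 0 |
| 2% | 0.160 | 0.032 | 0 |
| 5% | 0.677 | 0.248 | 0 |
| 10% | 0.974 | 0.677 | 0 |

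The zeros follow from the wording alone. Every other cell depends on the assumed p and f.

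**The case against.** A reader might infer that a bronchospastic reaction to the infusion can never reach the IMC. The documents do not support that. The exclusion is confined to the ad hoc trigger; exacerbations are reported as adverse events or serious adverse events (4.5.12) and so enter the periodic unblinded review. Section 5.3.5.1 keeps most infusion-timed symptoms countable. Section 5.3.5.10 speaks of a worsening of asthma, so a drug reaction does not become an exacerbation automatically.

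Nor is the periodic meeting the only safeguard. Grade 3 or higher allergic reactions are events of special interest, reported within 24 hours (5.2.3). Grade 3 or higher infusion signs that need treatment are notified to the Sponsor at once (4.3.2). Serious events are assessed against cumulative experience (5.7), and the code is broken for serious unexpected suspected reactions (4.2). The trigger is itself permissive, and the IMC Charter, not among the documents, may hold further triggers. All of this stands and limits the point. None of these routes is tied in the text to convening the IMC.

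A reader might also take the qualification in 4.6.1 as proof that the protocol restores related exacerbations in one place and forgets to in another. It does not: that clause refers to the other discontinuation criteria, not to relatedness.

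The best argument for the exclusion is noise. Table 4 makes related the default attribution, every patient had at least two exacerbations in the year before screening, and exacerbations are part of the primary endpoint. Some background events may therefore be judged related and prompt unblinded meetings. This is a fair cost that the documents do not allow one to quantify. It is limited by the serious or Grade 3+ condition, the three-patient threshold and the discretion to convene.

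Finally, the rates are assumed. The healthy-volunteer study reported only Grade 1 or 2 events in 106 people (1.2) and no infusion-related reactions (5.1.1.3). Those were not patients with asthma, but at 1% to 2% the trigger would be reached only 3% to 16% of the time even if every event counted. The blinded review also pools both arms, whereas the illustration uses the active arm alone.

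**Conclusion.** The point holds in a limited form. In the documents supplied, the only explicit ad hoc IMC trigger drops exacerbations judged related to study treatment. The events affected are related airway events recorded as exacerbations: those arising after 24 hours, and those within 24 hours for which 4.5.12 and 5.3.5.1 give no order of priority. The consequence is a possible wait for the next periodic review, at most about 3 months or about three infusions, with the other Sponsor reporting routes still in place. The probabilities only illustrate the assumed rates; they are not estimates for this drug. Recording by individual symptom may also spread one kind of reaction over several high level terms and make three in one term harder to reach, but that is a separate matter.

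**What to change.** 1. In Section 3.1.3 and the synopsis copy, limit the exclusion to asthma exacerbations not judged related to study treatment by the investigator or Sponsor. The three-patient threshold and the discretion to convene stay as they are.
2. Reconcile 3.1.3 with 4.5.12, 5.3.5.1 and 4.6.1, so that the protocol says how an event is classified when it meets the exacerbation definition and also falls within 24 hours of infusion.
3. In Section 5.7, name the anticipated events that the IMC is to monitor, or remove the reference.
4. Carry the same wording into the IMC Charter.

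The cost is a few clauses, a charter update and an occasional extra ad hoc meeting of an existing committee. No dose, stopping rule or patient-level management rule is proposed here.

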5.2.3 Adverse Events of Special Interest (Immediately Reportable to the Sponsor)

Adverse events of special interest are required to be reported by the investigator to the Sponsor immediately (i.e., no more than 24 hours after learning of the event; see Section [5.4.2](#) for reporting instructions). Adverse events of special interest for this study are as follows:

- Cases of potential drug-induced liver injury that include an elevated ALT or AST in combination with either an elevated bilirubin or clinical jaundice, as defined by Hy's Law (see Section [5.3.5.7](#))
- Suspected transmission of an infectious agent by the study drug, as defined below
 - Any organism, virus, or infectious particle (e.g., prion protein transmitting transmissible spongiform encephalopathy), pathogenic or non-pathogenic, is

considered an infectious agent. A transmission of an infectious agent may be suspected from clinical symptoms or laboratory findings that indicate an infection in a patient exposed to a medicinal product. This term applies only when a contamination of the study drug is suspected.

- Grade ≥ 3 allergic reaction within 24 hours of infusion or suspected to be due to study drug

Grade ≥ 3 allergic reactions include generalized urticaria and angioedema (Grade 3) and anaphylaxis (Grade 4).

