5.3.5.1 Infusion-Related or Injection Reactions

Adverse events that occur during or within 24 hours after study drug administration should be captured as individual signs and symptoms on the Adverse Event eCRF rather than an overall diagnosis (e.g., record dyspnea and hypotension as separate events rather than a diagnosis of infusion-related or anaphylactic reaction).

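### The ad hoc IMC trigger counts patients within one MedDRA high level term, but acute reactions are recorded symptom by symptom, so three severe reactions may fail to meet it

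*Protocol*

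**What the plan says.** Three parts of the protocol bear on this.

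- **The trigger (3.1.3, repeated in the synopsis).** Under this section, "ad-hoc IMC meetings may be convened immediately or expeditiously at any time to address potential safety concerns". The only written condition is that periodic blinded review shows three or more patients with serious or Grade 3+ events, asthma exacerbations excluded, that the investigator or Sponsor "determines to be related to study treatment, within the same MedDRA high level term". Scheduled IMC meetings are held "no less frequently than once every 3 months".
- **The recording rule (5.3.5.1).** Events during or within 24 hours of dosing "should be captured as individual signs and symptoms on the Adverse Event eCRF rather than an overall diagnosis". The protocol's own example tells the site to "record dyspnea and hypotension as separate events rather than a diagnosis of infusion-related or anaphylactic reaction". Section 5.3.5.2 exempts infusion-related and injection reactions from the general rule that a known diagnosis is recorded.
- **The AESI (5.2.3).** One category is "Grade ≥ 3 allergic reaction within 24 hours of infusion or suspected to be due to study drug". It is reportable to the Sponsor within 24 hours. Here the unit is the reaction, not the symptom.

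Section 5.1.1 gives hypersensitivity and injection-site or infusion-related reactions as the drug's potential risk and says the data suggest no additional ones.

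**The concern.** A trigger that counts patients within one coding group works only if patients with the same harm land in the same group. For acute reactions the recording rule works against this. One patient's reaction may be entered as hypotension, another's as dyspnea and a third's as angioedema. If those terms sit under different high level terms, three patients with the same syndrome give a count of one in each. No section adds them back together.

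What is at stake is the speed with which unblinded data are examined for the risk that the protocol itself names. If the trigger is missed and nothing else prompts a meeting, the next scheduled review may be up to 3 months away. At one infusion every 4 weeks that is about three further infusions per patient (13 weeks / 4 = 3.25).

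**Working it through.** The documents state no operating characteristic for the trigger, so there is no figure to reproduce. The check asks how likely three severe related acute reactions are to meet the rule.

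**Inputs from the documents.** Three patients and one high level term (3.1.3); symptom-level entry within 24 hours (5.3.5.1); 69 patients dosed with active drug (SAP Output 1.1).

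**Inputs not in the documents, so assumed.** K is the number of high level terms over which reaction symptoms spread, taken as 4 to 20. m is the number of different terms per reaction that qualify by being serious or Grade 3+, taken as 1 to 4. The documents reproduce no part of the MedDRA hierarchy. That the symptoms fall under different terms at all is part of this assumption.

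**Formula.** If each reaction draws m distinct terms out of K, evenly and independently, the chance that all three patients share at least one term is, by inclusion-exclusion,

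P = Σ (j = 1 to m) (−1)^(j+1) · C(K, j) · [C(K−j, m−j) / C(K, m)]³

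Worked cases:

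- K = 6, m = 2: 6·(5/15)³ − 15·(1/15)³ = 0.2222 − 0.0044 = 0.218
- K = 6, m = 3: 6·(10/20)³ − 15·(4/20)³ + 20·(1/20)³ = 0.75 − 0.12 + 0.0025 = 0.6325
- K = 4, m = 3: 4·(3/4)³ − 6·(2/4)³ + 4·(1/4)³ = 1.6875 − 0.75 + 0.0625 = 1. Each reaction misses only one of the four terms, so three reactions always share one.
- K = 20, m = 1: 20·(1/20)³ = 0.0025

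Probability that three reactions meet the one-term rule:

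| K | m = 1 | m = 2 | m = 3 | m = 4 |
|---|---|---|---|---|
| 4 | 0.063 | 0.472 | 1.000 | 1.000 |
| 6 | 0.028 | 0.218 | 0.633 | 0.973 |
| 8 | 0.016 | 0.124 | 0.388 | 0.745 |
| 10 | 0.010 | 0.080 | 0.257 | 0.538 |
| 20 | 0.003 | 0.020 | 0.067 | 0.154 |

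The probability drops below one half once K reaches 2, 4, 7 or 11 for m = 1, 2, 3 or 4.

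**If spread is not even.** Suppose one term is present in a share p of reactions and no other term is shared. Then P = p³: 0.5³ = 0.125, 0.8³ = 0.512, 0.9³ = 0.729.

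**More than three reactions (simulation, K = 10, m = 2).** The chance is 0.27 at four reactions, 0.51 at five and 0.75 at six. Under even spread a miss at three is often a delay rather than a permanent loss.

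**Across the active arm.** With 69 patients and assumed severe-reaction rates of 2%, 5% and 10%, the binomial chance of at least three reactions is 16.0%, 67.7% and 97.4%. A patient-level count would be met that often. The one-term rule is met in 2.7%, 24.1% and 73.8% with K = 10, m = 2 (simulation), and with no loss when K = 4, m = 3.

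**What moves m.** Only symptoms that are themselves serious or Grade 3+ count. In Appendix 7 anaphylaxis is Grade 4, but acute bronchospasm that normalizes with a bronchodilator and hypotension correctable with oral fluids are each Grade 2. Splitting can therefore lower m. Marking every symptom of a serious reaction as serious would raise it.

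**The case against.** A reader might infer that three severe reactions would usually fail to trip the trigger, or that it cannot add them up. Neither follows. The table runs from 0.003 to 1.000, and K and m are not in the documents. Even, independent spread also tends to understate overlap: reactions with a common mechanism may share a leading symptom, Appendix 6 lists only four organ systems for anaphylaxis, and 5.2.3 names only generalized urticaria and angioedema as Grade 3 allergic reactions.

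A reader might also infer that routine IMC review is the only fallback. It is not:

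- Section 4.3.2 requires immediate sponsor notification of Grade 3+ infusion-related signs or symptoms that need treatment.
- Section 5.2.3 requires AESI reports within 24 hours.
- Section 5.7 commits the Sponsor to prompt evaluation of serious events and AESIs.
- Under 4.2, Drug Safety breaks the code for serious unexpected suspected reactions.
- The trigger is itself permissive, and an IMC that meets also weighs "the similarity and frequency of events under a single higher level term, the plausibility of a common mechanism".

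The scope is narrow as well. The splitting rule covers only the first 24 hours. Later allergic events fall under the diagnosis rule in 5.3.5.2, although the position of delayed infusion-related reactions, which 5.1.1.3 recognizes up to 14 days, is unclear. Phase I saw no infusion-related or systemic hypersensitivity reactions, enrollment has halted, and the IMC charter, not among these documents, may already group such terms.

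All of this stands and limits the consequence. What it does not supply is a link from a number of reactions to a meeting of the unblinded committee. The aggregate-signal clause in 4.6.3 refers back to 3.1.3. The AESI and anaphylaxis summaries in 6.5 are analysis outputs, not alarms. A permissive rule still tells those reviewing blinded data what to count.

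**Conclusion.** The mismatch is in the text: the trigger counts within one high level term, acute reactions are entered as separate symptoms, and no section regroups them. Three patients with severe acute reactions may fail to meet the trigger. How often is unknown; the range is under 1% to 100% under assumed values of K and m, and no single figure within it should be quoted as the trial's. The conclusion needs only that some reaction symptoms code to different high level terms. It applies to reactions during or within 24 hours of dosing. With the other reporting routes in place, this is a gap in one alarm rather than an absence of safety oversight. It is worth closing because the remedy is cheap and uses data already collected.

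**What to change.** Reconcile 3.1.3, 5.2.3 and 5.3.5.1. Keep the high-level-term rule and add to 3.1.3, the matching synopsis text and the IMC charter that the ad hoc trigger is also met by three or more patients with the Grade 3+ allergic reaction AESI of 5.2.3, each patient counted once whatever symptom terms were coded.

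State two things with it:

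- whether the relatedness condition applies to this count, since the 24-hour limb of the AESI does not require it;
- whether serious or Grade 3+ infusion-related reactions that are not allergic are also counted by patient, since the AESI does not cover them.

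Under such a count, three qualifying patients meet the trigger with certainty. The cost is one added rule with these two clarifications; AESI reports already reach the Sponsor within 24 hours, so no new data are needed. The downside is possibly an extra ad hoc meeting, because a reaction within 24 hours of infusion would count even if judged unrelated, unless relatedness is required.
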